13 PUBLICATION POLICY

The Sponsor and Investigator will mutually manage the publication and presentation process. All manuscripts, abstracts, or other modes of presentation arising from the results of the study must be reviewed and approved in writing by the Sponsor in advance of submission in accordance with the

clinical site agreement. The review is aimed at protecting the Sponsor's proprietary information existing either at the date of the commencement of the study or generated during the study.

The Sponsor will register the study on a public registry and results database of clinical trials.

The Sponsor will publish the summary study results in EudraCT within six months following the end of the trial.

The Sponsor and the Investigator will disclose the study results, in the form of a clinical study synopsis to the Health Authorities and the EC / IRB respectively, within 1 year of the end of the study. The format of this synopsis and that of the clinical study report will comply with the ICH3 guidelines for the structure and content of a clinical study report.

APPENDIX 1: IBS-QOL

PLEASE WRITE IN

TODAY'S DATE:

Month Day Year

PLEASE READ THIS CAREFULLY

On the following pages you will find statements concerning bowel problems (irritable bowel syndrome) and how they affect you.

For each statement, please choose the response that applies best to you and **circle** the number of your response.

IF YOU ARE UNSURE ABOUT HOW TO RESPOND TO A STATEMENT, PLEASE GIVE THE BEST RESPONSE YOU CAN. **THERE ARE NO RIGHT OR WRONG RESPONSES.**

YOUR RESPONSES WILL BE KEPT STRICTLY CONFIDENTIAL.

IF YOU HAVE ANY QUESTIONS, PLEASE CONTACT:

SITE ADDRESS AND PHONE NUMBER TO BE PLACED HERE

Authors hold joint copyright over the IBS-QOL and all its translations.

PARTICIPANT ID:

Page 53 of 137

About how you feel

Please think about your life over the **past month (last 30 days)** and look at the statements below. Each statement has five different responses. For each statement, please circle the response that best describes your feelings.

Q1. I feel helpless because of my bowel problems. (Please circle one number)

- 1 NOT AT ALL
- 2 SLIGHTLY
- **3** MODERATELY
- 4 QUITE A BIT
- **5** EXTREMELY

Q2. I am embarrassed by the smell caused by my bowel problems. *(Please circle one number)*

- 1 NOT AT ALL
- 2 SLIGHTLY
- **3** MODERATELY
- 4 QUITE A BIT
- 5 EXTREMELY

Q3. I am bothered by how much time I spend on the toilet. (Please circle one number)

- 1 NOT AT ALL
- 2 SLIGHTLY
- **3** MODERATELY
- 4 QUITE A BIT
- 5 A GREAT DEAL

Q4. I feel vulnerable to other illnesses because of my bowel problems. (*Please circle one number*)

- 1 NOT AT ALL
- 2 SLIGHTLY
- **3** MODERATELY
- 4 QUITE A BIT
- 5 EXTREMELY

Q5. I feel fat/bloated because of my bowel problems. (Please circle one number)

- 1 NOT AT ALL
- 2 SLIGHTLY
- 3 MODERATELY
- 4 QUITE A BIT
- 5 A GREAT DEAL

Q6. I feel like I'm losing control of my life because of my bowel problems. (*Please circle one number*)

- 1 NOT AT ALL
- 2 SLIGHTLY
- **3** MODERATELY
- 4 QUITE A BIT
- 5 A GREAT DEAL

Q7. I feel my life is less enjoyable because of my bowel problems. (*Please circle one number*)

- 1 NOT AT ALL
- 2 SLIGHTLY
- **3** MODERATELY
- 4 QUITE A BIT
- 5 A GREAT DEAL

Q8. I feel uncomfortable when I talk about my bowel problems. (Please circle one number)

- 1 NOT AT ALL
- 2 SLIGHTLY
- **3** MODERATELY
- 4 QUITE A BIT
- 5 EXTREMELY
- Q9. I feel depressed about my bowel problems. (Please circle one number)
 - 1 NOT AT ALL
 - 2 SLIGHTLY
 - **3** MODERATELY
 - 4 QUITE A BIT

5 EXTREMELY

Q10. I feel isolated from others because of my bowel problems. (Please circle one number)

- 1 NOT AT ALL
- 2 SLIGHTLY
- 3 MODERATELY
- 4 QUITE A BIT
- 5 EXTREMELY

Q11. I have to watch the amount of food I eat because of my bowel problems. (*Please circle one number*)

- 1 NOT AT ALL
- 2 SLIGHTLY
- 3 MODERATELY
- 4 QUITE A BIT
- 5 A GREAT DEAL

Q12. Because of my bowel problems, sexual activity is difficult for me. (*Please circle one number*)

(If not applicable, please circle "NOT AT ALL")

- 1 NOT AT ALL
- 2 SLIGHTLY
- **3** MODERATELY
- 4 QUITE A BIT
- **5** EXTREMELY

Q13. I feel angry that I have bowel problems. *(Please circle one number)*

- 1 NOT AT ALL
- 2 SLIGHTLY
- **3** MODERATELY
- 4 QUITE A BIT
- 5 EXTREMELY

Q14. I feel like I irritate others because of my bowel problems. (Please circle one number)

- 1 NOT AT ALL
- 2 SLIGHTLY
- 3 MODERATELY
- 4 QUITE A BIT
- 5 A GREAT DEAL

Q15. I worry that my bowel problems will get worse. (Please circle one number)

- 1 NOT AT ALL
- 2 SLIGHTLY
- **3** MODERATELY
- 4 QUITE A BIT
- 5 A GREAT DEAL
- Q16. I feel irritable because of my bowel problems. (Please circle one number)
 - 1 NOT AT ALL
 - 2 SLIGHTLY
 - **3** MODERATELY
 - 4 QUITE A BIT
 - 5 EXTREMELY

Q17. I worry that people think I exaggerate my bowel problems. (Please circle one number)

- 1 NOT AT ALL
- 2 SLIGHTLY
- **3** MODERATELY
- 4 QUITE A BIT
- 5 À GREAT DEAL
- Q18. I feel I get less done because of my bowel problems. (Please circle one number)
 - 1 NOT AT ALL
 - 2 SLIGHTLY
 - **3** MODERATELY
 - 4 QUITE A BIT

5 A GREAT DEAL

Q19. I have to avoid stressful situations because of my bowel problems. (*Please circle one number*)

- 1 NOT AT ALL
- 2 SLIGHTLY
- **3** MODERATELY
- 4 QUITE A BIT
- 5 A GREAT DEAL

Q20. My bowel problems reduce my sexual desire. (Please circle one number)

- 1 NOT AT ALL
- 2 SLIGHTLY
- 3 MODERATELY
- 4 QUITE A BIT
- 5 A GREAT DEAL

Q21. My bowel problems limit what I can wear. (*Please circle one number*)

- 1 NOT AT ALL
- 2 SLIGHTLY
- **3** MODERATELY
- 4 QUITE A BIT
- 5 A GREAT DEAL

Q22. I have to avoid strenuous activity because of my bowel problems. (*Please circle one number*)

- 1 NOT AT ALL
- 2 SLIGHTLY
- **3** MODERATELY
- 4 QUITE A BIT
- 5 A GREAT DEAL

Q23. I have to watch the kind of food I eat because of my bowel problems. (*Please circle one number*)

- 1 NOT AT ALL
- 2 SLIGHTLY
- 3 MODERATELY
- 4 QUITE A BIT
- 5 A GREAT DEAL

Q24. Because of my bowel problems, I have difficulty being around people I do not know well. (*Please circle one number*)

- 1 NOT AT ALL
- 2 SLIGHTLY
- **3** MODERATELY
- 4 QUITE A BIT
- 5 A GREAT DEAL

Q25. I feel sluggish because of my bowel problems. (Please circle one number)

- 1 NOT AT ALL
- 2 SLIGHTLY
- **3** MODERATELY
- 4 QUITE A BIT
- **5** EXTREMELY

Q26. I feel unclean because of my bowel problems. (Please circle one number)

- 1 NOT AT ALL
- 2 SLIGHTLY
- **3** MODERATELY
- 4 QUITE A BIT
- 5 EXTREMELY

Q27. Long trips are difficult for me because of my bowel problems. (*Please circle one number*)

- 1 NOT AT ALL
- 2 SLIGHTLY
- **3** MODERATELY
- 4 QUITE A BIT
- 5 EXTREMELY

Q28. I feel frustrated that I cannot eat when I want because of my bowel problems. (*Please circle one number*)

- 1 NOT AT ALL
- 2 SLIGHTLY
- **3** MODERATELY
- 4 QUITE A BIT
- 5 EXTREMELY

Q29. It is important to be near a toilet because of my bowel problems. (*Please circle one number*)

- 1 NOT AT ALL
- 2 SLIGHTLY
- 3 MODERATELY
- 4 QUITE A BIT
- 5 EXTREMELY

Q30. My life revolves around my bowel problems. (Please circle one number)

- 1 NOT AT ALL
- 2 SLIGHTLY
- **3** MODERATELY
- 4 QUITE A BIT
- 5 A GREAT DEAL

Q31. I worry about losing control of my bowels. (*Please circle one number*)

- 1 NOT AT ALL
- 2 SLIGHTLY
- 3 MODERATELY
- 4 QUITE A BIT
- 5 A GREAT DEAL

Q32. I fear that I won't be able to have a bowel movement. (Please circle one number)

- 1 NOT AT ALL
- 2 SLIGHTLY
- **3** MODERATELY
- 4 QUITE A BIT
- 5 A GREAT DEAL
- Q33. My bowel problems are affecting my closest relationships. (Please circle one number)
 - 1 NOT AT ALL
 - 2 SLIGHTLY
 - **3** MODERATELY
 - 4 QUITE A BIT
 - 5 A GREAT DEAL
- Q34. I feel that no one understands my bowel problems. (*Please circle one number*)
 - 1 NOT AT ALL
 - 2 SLIGHTLY
 - 3 MODERATELY
 - 4 QUITE A BIT
 - **5** EXTREMELY

APPENDIX 2: HOSPITAL ANXIETY AND DEPRESSION SCALE (HADS)

[figure not shown]
Instructions: Doctors are aware that emotions play an important part in most illnesses. If your doctor knows about these feelings he or she will be able to help you more. This questionnaire is designed to help your doctor know how you feel. Read each item and circle the reply which comes closest to how you have been feeling in the past week. Don't take too long over your replies: your immediate reaction to each item will probably be more accurate than a long thought out response.

I feel tense or 'wound up':	A	I feel as if I am slowed down:	D
Most of the time	3	Nearly all of the time	3
A lot of the time	2	Very often	2
Time to time, occasionally	1	Sometimes	1
Not at all	0	Not at all	0
I still enjoy the things I used to enjoy:	D	I get a sort of frightened feeling like 'butterflies in the stomach':	A
Definitely as much	0	Not at all	0
Not quite so much	1	Occasionally	1
Only a little	2	Quite often	2
Not at all	3	Very often	3
I get a sort of frightened feeling like	A	I have lost interest in my	D
something awful is about to happen:	3	appearance: Definitely	3
Very definitely and quite badly		I don't take as much care as I should	
Yes, but not too badly	2		2
A little, but it doesn't worry me	1	I may not take quite as much care	1
Not at all	0	I take just as much care as ever	0
I can laugh and see the funny side of things:	D	I feel restless as if I have to be on the move:	A
As much as I always could	0	Very much indeed	3
Not quite so much now	1	Quite a lot	2
Definitely not so much now	2	Not very much	1
Not at all	3	Not at all	0

Worrying thoughts go through m mind:	y A	I look forward with enjoyment to I things:)
A great deal of the time	3	A much as I ever did 0)
A lot of the time	2	Rather less than I used to 1	1
From time to time but not too often	1	Definitely less than I used to 3	3
Only occasionally	0	Hardly at all 2	2
I feel cheerful:	D	I get sudden feelings of panic: A	4
Not at all	3	Very often indeed 3	3
Not often	2	Quite often 2	2
Sometimes	1	Not very often 1	1
Most of the time	0	Not at all 0	0
I can sit at ease and feel relaxed:	Α	I can enjoy a good book or radio I or TV programme:)
Definitely	0	Often ()
Usually	1	Sometimes 1	1
Not often	2	Not often 2	2
Not at all	3	Very seldom 3	3

[figure not shown]
Questions relating to anxiety are indicated by an 'A' while those relating to depression are shown by a 'D'. Scores of 0-7 in respective subscales are considered normal, with 8-10 borderline and 11 or over indicating clinical 'caseness'

[figure not shown]

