Subjects will be asked to complete a quality of life questionnaire consisting of 34 questions with a five-point response. The individual responses to the 34 items are summed and averaged for a total score and then transformed to a 0-100 scale for ease of interpretation with higher scores indicating better IBS specific quality of life. Once subjects are randomised they will be asked to record their score on their smartphone at each clinic visit or within 24hrs prior to the Clinic Visit.

Hospital Anxiety and Depression Score (HADS) (Appendix 2)

Subjects will be asked to complete HADS which is a 14-item scale that generates ordinal data. Seven of the items relate to anxiety and 7 relate to depression. Each item is scored from 0-3 so a subject can score 0 to 21 for either anxiety or depression. Once subjects are randomised they will be asked to complete this questionnaire on their smartphone at each clinic visit or within 24hrs prior to the Clinic Visit.

Bristol Stool Chart

Subjects will be asked to record stool frequency and consistency. Stool types will be based on the Bristol Stool Chart (Appendix 3). This data will be recorded daily for a 7-day period up to Baseline (Visit 1) to allow Subject to be classified into Cohorts of IBS sub-types. Once subjects are randomised they will be asked to record their stool frequency daily up to 10 bowel movements per day and score each stool type on their smartphone. No bowel movements in any given day will also be recorded.

Stool frequency will be defined as a sum of weekly CSBMs. Stool frequency will be recorded using the following question: "How many times did you open your bowels during the past 24 hours? If you have not had any bowel movements today, please enter 0." Subjects will be reminded to rate all of their bowel movements in the Bristol Stool Chart before answering the question. CSBMs will be determined by absence of laxative use recorded in concomitant medication questions for the same 24 hour period.

IBS Symptom Severity Score (SSS) (Appendix 4)

Subjects will be asked to complete a questionnaire on severity of abdominal distension, severity of abdominal pain, frequency of abdominal pain, dissatisfaction with bowel habits, and interference of IBS symptoms with daily life. A score ranging from 0 (no symptoms) to 500 (maximum severity) can be achieved as mild (74-174), moderate (175-299) or severe (>300) IBS symptoms.

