#### 10.1.2.5 Hospital Anxiety and Depression Scale

The Hospital Anxiety and Depression Scale (HADS) is commonly used by doctors to determine the levels of anxiety and depression that a person is experiencing. The scale consists of a series of statements about which subjects must respond with their feelings. Each statement has a set of ordinal responses with scores 0 to 3 or 3 to 0.

Some statements correspond with anxiety and some with depression, as given in the table below.

| Statement   | Characteristic |
|---|----------------|
| I feel tense or wound up  | Anxiety        |
| I get a sort of anxious feeling like butterflies in the stomach             | Anxiety        |
| I get a sort of frightened feeling as if something awful is about to happen | Anxiety        |
| I feel restless as if I have to be on the move                              | Anxiety        |
| Worrying thoughts go through my mind  | Anxiety        |
| I get sudden feelings of panic  | Anxiety        |
| I can sit at ease and feel relaxed  | Anxiety        |
| I feel as if I am slowed down   | Depression     |
| I enjoy the things I used to enjoy  | Depression     |
| I have lost interest in my appearance                                       | Depression     |
| I can laugh and see the funny side of things                                | Depression     |
| I look forward with enjoyment to things                                     | Depression     |
| I feel cheerful   | Depression     |
| I can enjoy a good book, radio or television program                        | Depression     |

[figure not shown]
An Anxiety and a Depression Total Score ranging from 0 to 21 each are derived by summing the individual scores under each category. The Total Scores are interpreted as:

0-7 = Normal,  
 8-10 = Borderline abnormal (borderline case)  
 11-21 = Abnormal (case)

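### Protocol Appendix 2 scores one HADS depression item 0, 1, 3, 2, against the SAP's ordinal rule; wherever that key is used, the depression total is off by 1 point for the two worst replies

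*Protocol*

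**What the plan says.** HADS is a secondary efficacy endpoint (Protocol 3.2), completed on the smartphone (Protocol 7.1). The schedule of assessments places it at Baseline, Week 4, Week 8 and Follow-up.

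On scoring, Protocol 7.1 says: "Each item is scored from 0-3 so a subject can score 0 to 21 for either anxiety or depression". SAP 10.1.2.5 says: "Each statement has a set of ordinal responses with scores 0 to 3 or 3 to 0", and then: "An Anxiety and a Depression Total Score ranging from 0 to 21 each are derived by summing the individual scores under each category". The SAP table assigns each statement to anxiety or depression, and "I look forward with enjoyment to things" is a depression item. The SAP does not list a score for each reply.

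The only place that does is the form in Protocol Appendix 2. For this item it prints, from best to worst reply:

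- Reply 1: "A much as I ever did 0"
- Reply 2: "Rather less than I used to 1"
- Reply 3: "Definitely less than I used to 3"
- Reply 4: "Hardly at all 2"

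SAP 11.3.5 summarises mean anxiety and depression scores and mean changes from baseline. It adds t-tests of the change at each post-baseline visit, labelled exploratory.

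**The concern.** The four replies are in order of severity, but the last two scores are not: the worst answer scores lower than the second worst. The sequence 0, 1, 3, 2 is neither of the two orders that the SAP allows.

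The SAP sums whatever item scores it receives and supplies no key to check them against. A programmer who needs reply-level codes will find them only in Appendix 2. If those codes are used, a subject who gets worse from reply 3 to reply 4 is recorded as improving on this item. A wrong baseline score also carries into every later change score for that subject.

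**Working it through.** **Inputs.** Printed scores for the item: 0, 1, 3, 2 (Protocol Appendix 2). Ordered scores: 0, 1, 2, 3 (SAP 10.1.2.5). Seven depression items, each 0 to 3 (Protocol 7.1). Cut-offs: 0-7, 8-10, and 11 or over (Protocol Appendix 2 and SAP 10.1.2.5).

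**Step 1: the stated range.** 7 × 3 = 21, so the range is 0 to 21. With the printed scores the range is still 0 to 21, because reply 3 supplies the 3. A range check would therefore not find the swap. The worst answer on all seven items totals 6 × 3 + 3 = 21 in order, but 6 × 3 + 2 = 20 as printed.

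**Step 2: the other items.** The remaining 13 items on the form run strictly 0 to 3 or 3 to 0. Only this one departs.

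**Step 3: error in one assessment** (printed minus ordered).

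| Reply | Printed | Ordered | Error |
|---|---|---|---|
| 1 | 0 | 0 | 0 |
| 2 | 1 | 1 | 0 |
| 3 | 3 | 2 | +1 |
| 4 | 2 | 3 | -1 |

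**Step 4: error in change from baseline** (error at the visit minus error at baseline).

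| Move | Printed change | Ordered change | Error |
|---|---|---|---|
| Reply 3 to 4 (worse) | 2 - 3 = -1 | 3 - 2 = +1 | -2 |
| Reply 4 to 3 (better) | 3 - 2 = +1 | 2 - 3 = -1 | +2 |
| Reply 1 or 2 to 3, or 4 to 1 or 2 | | | +1 |
| Reply 1 or 2 to 4, or 3 to 1 or 2 | | | -1 |
| Same reply, or between 1 and 2 | | | 0 |

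Only the moves between replies 3 and 4 reverse the sign of the item change.

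**Step 5: cut-offs.** Enumerating all 4^7 = 16,384 answer patterns, a category changes only where the ordered total of 7 becomes 8, 8 becomes 7, 10 becomes 11, or 11 becomes 10. This happens in 216 + 216 + 546 + 546 = 1,524 patterns. That is a count of patterns, not an estimate of how many subjects would be affected.

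**Step 6: group means.** Error in a group mean = p3 - p4, where p3 and p4 are the proportions choosing replies 3 and 4. The documents give no reply frequencies, so these are assumptions.

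| p3 | p4 | Error in mean |
|---|---|---|
| 0.15 | 0.05 | +0.10 |
| 0.20 | 0.10 | +0.10 |
| 0.10 | 0.10 | 0.00 |
| 0.10 | 0.20 | -0.10 |

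The most uneven pairing within these ranges gives 0.20 - 0.05 = +0.15. The same key would apply to both arms, so the error in a between-arm difference at a visit is the difference between the arms in p3 - p4. It is zero if the arms answer alike.

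**The case against.** **The app may not use this key.** HADS is captured on a smartphone, and neither the app's item codes nor the export specification is in the documents. If the SAP's ordered rule was programmed, the totals are right. This stands. A reader might infer from the form that the trial's depression totals are wrong; the documents do not support that. They show a wrong printed key and a contradiction, not its use.

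**The sequence may be an artefact of reading the PDF.** The table is visibly damaged in places: some scores are detached from their replies, and some characters near this item are garbled. The scores in this column also appear twice, so the repetition is not independent confirmation. Some doubt therefore remains until the printed page is looked at. A misprint is still much the likelier explanation. The reply labels are in order, the item on the left of the same rows reads 3, 2, 1, 0, and the items below in the same column read correctly. A reading fault would have had to exchange two scores and leave everything around them intact.

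**Category errors harm no planned analysis.** A reader might infer that misclassification as normal, borderline or case would distort a result. SAP 11.3.5 specifies means, changes and t-tests only, so the cut-offs serve as interpretive text. This stands.

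**The tests are exploratory and the errors offset each other.** Also true, and it limits the size of the point. It does not justify leaving the only reply-level key in conflict with the SAP.

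**Conclusion.** The point holds as a conditional error in the scoring key. Appendix 2 contradicts SAP 10.1.2.5 on one of seven depression items. Where the printed key is applied, the total is wrong by +1 for reply 3 and -1 for reply 4, and a change between them is wrong by 2 points with the sign reversed.

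The group-level effect is small: about -0.1 to +0.1 points on a 21-point scale in the four combinations tried, and +0.15 at the most uneven pairing. It is confined to the depression means, changes and exploratory t-tests. The anxiety score and the primary endpoint are unaffected.

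The conclusion rests on two things that the documents cannot settle: that the form is printed as it reads, and whether the app or the analysis dataset follows it. It should be corrected because an incorrect key would pass a range check and is easy to put right before lock.

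**What to change.** 1. Correct Protocol Appendix 2 so that this item scores 0, 1, 2, 3. Protocol Appendix 13 records that all patients had been randomised by version 3.1, so this mainly puts the reference right rather than changing data collection.
2. State the score for every reply to all 14 items in SAP 10.1.2.5, so that the derivation does not depend on the form.
3. Before lock, check the eCOA build and export against that key. The listing of all HADS responses and derived scores already planned in SAP 11.3.5 can support the check.
4. If the printed codes were used, exchange 2 and 3 for this item in the item-level data and re-derive the depression totals and changes. The swap is one-to-one, so it is fully reversible from item-level codes and does not require the reply text to have been stored. If the build already used the ordered codes, change nothing, since a swap would introduce the error.

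The cost is one appendix correction, a short addition to the SAP and a brief programming check. No new data are needed.

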APPENDIX 3: BRISTOL STOOL CHART

APPENDIX 4: IBS-SSS

IBS QUESTIONNAIRE							
	G.P. Name: Address:						
Date of birth:							
Marital status: Single / Married / Divorced / Occupation:							
This form is designed to enable us to record a expected that your symptoms might vary ov	And monitor the severity of your IBS. It is to be er time, so please try and answer the questions ast ten days or so). All information will be kept						
	nt responses are a possibility please circle the						
2. Some questions will require you to write in	n an appropriate response.						
3. Some questions require you to put a cross of a particular problem.	on a line which enables us to judge the severity						
For example:							
How severe was your pain?							

[figure not shown]

			y how much your Irritable th your life in general.	
0 %			100 %	
not at all	not much	quite a lot	completely	
		I	BS SEVERITY SCORE:	
		2		

PART 2: OTHER IBS DATA									
BOWEL HABIT									
5. a) What is the most number of times you open your bowels per day/week/month?									
	Number of times per day / week / month (Circle appropriate)								
	Note: For some people the answer to part a and b could be the same								
b)	What is the least number of times you	n open your bowels per day.	/week/month?						
	Number of times per day	/ week / month (Circle ap	ppropriate)						
6 . In	the following questions you may circle r	nore than one answer:							
	re your motions ever:								
a)	normal	often / occasionally / never	(Circle appropriate)						
b)	hard	often / occasionally / never	(Circle appropriate)						
c)	very thin (like string)	often / occasionally / never	(Circle appropriate)						
d)	in small pieces (like rabbit pellets)	often / occasionally / never	(Circle appropriate)						
e)	mushy (like porridge)often / occasionally / never(Circle appropriate)								
Ŋ	watery often / occasionally / (Circle never appropriate)								
7. In the following questions you may circle more than one answer:									
Da	o you ever:								
			Circle appropriate box						
a)	pass mucus (or slime or jelly) with yo	ur motions	YES NO						

b)	pass blood with your motions	YES NO
c)	have to hurry/rush to the toilet to open your bowels	YES NO
d)	strain to open your bowels	YES NO
e)	feel you haven't emptied your bowel after you have passed a motion	completely YES NO
	3	

